## Data Analysis

The summary of the demographic characteristics will be presented. Continuous variables will be summarized using mean (SD) or median (interquartile range) depending on whether or not the data follow the normal distribution. Categorical variables will be summarized by frequency (percentage). Comparison of continuous variables between any independent groups will be examined using two-sided t-test or two-sided Wilcoxon rank sum test, analysis of variance (ANOVA) or Kruskal-Wallis test followed by pairwise tests, as appropriate. Categorical variables will be examined using Fisher's exact test or Pearson's Chi-square test, as appropriate.

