**Statement of Investigator**

# **Parkinson's Disease Inpatient Clinical Knowledge and management**

*An observational, quasi-experimental retrospective and prospective study.*

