## **Sample Size Calculation**

A total of 433 patients were admitted to Hackensack University Medical Center with a diagnosis of PD in the year 2014. A convenience sample of 300 patients, 150 patients in the prospective phase and 150 patients in the retrospective phase, and approximately 346 clinicians, before and after implementing the Parkinson's Disease Inpatient Clinical Knowledge and Management education program will be enrolled in the study.

The sample of clinicians will include physician's assistant, advanced practice nurses, staff nurses, nurse educators, case managers, dietitians, pharmacists, physical therapist and occupational therapist. (Table 1)

Categories	Overall population	Sample population	Percentage (Sample size)
Staff Nurses Adult (Inpatient Units)	1931	100	5 %
Nursing Assistants	277	N/A	
Patient Care Technicians	165	N/A	
Advanced Practice Nurses (Adult Inpatient Units)	107	87	81%
Case Managers(Adult Inpatient Units)	48	48	100%
Nurse Educator Adult Inpatient	20	19	95%
Physician's Assistant Adult Inpatient	73	40	54%
Dietitians	17	17	100%
Pharmacists	119	12	11%
Physical Therapist	17	17	100%
Occupational Therapists	6	6	100%

Table 1

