## Measurements

The following will be documented on a case report form: demographics (age, sex, and race), comorbidities and complications, date of discharge, length of stay, and number of medication discrepancies.

- Subject ID (coded de-identified patient identifier)
- Demographics (age race, gender)
- Primary Diagnosis
- Comorbidities
- Medication list at admission (Admission Medication Reconciliation)
  - Number of medications at admission
- Prescribed Medication List (Medication Administration Record)
  - Number of medications during hospitalization
- Medication list at discharge (Discharge Medication Reconciliation)
- Complications associated with medication administration
- Medication Administration Schedule
  - Order Time
  - Patient Falls
  - Number of falls
  - Time of patient falls
  - Injury
- Length of Stay

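### The seven secondary patient endpoints are compared between two non-randomised cohorts with unadjusted tests only, so measured case-mix differences can be read as an intervention effect

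*Combined protocol and SAP*

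**What the plan says.** The Statement of Investigator page describes the design as "An observational, quasi-experimental retrospective and prospective study". Sample Size Calculation gives "A convenience sample of 300 patients, 150 patients in the prospective phase and 150 patients in the retrospective phase". The Retrospective Study Period section takes the first cohort from an EPIC report on adult admissions with a Parkinson's diagnosis in January to June 2015. The second cohort is recruited later, from patients who consent, are alert and will wear the smartwatch (Inclusion Criteria, Exclusion Criteria, Study Enrollment Procedure).

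Data Analysis is a single paragraph. Demographics are to be summarised. For outcomes it states: "Comparison of continuous variables between any independent groups will be examined using two-sided t-test or two-sided Wilcoxon rank sum test". For several groups it adds "analysis of variance (ANOVA) or Kruskal-Wallis test followed by pairwise tests, as appropriate", and for the rest "Categorical variables will be examined using Fisher's exact test or Pearson's Chi-square test, as appropriate". Regression, covariates, matching, weighting and stratification appear nowhere in the document.

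Measurements puts on the case report form "demographics (age, sex, and race), comorbidities and complications, date of discharge, length of stay, and number of medication discrepancies". Its itemised list adds primary diagnosis, the admission medication list and "Number of medications at admission". Limitations names the single site and the convenience sample, but not confounding.

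**The concern.** All seven items under Secondary Endpoints (medication timing, medication errors, contraindicated drugs, falls, confusion scores, delirium scores and length of stay) rest on this comparison. Nothing in the design balances the cohorts. Eligibility is also wide: Parkinson's disease may be the primary or a secondary diagnosis, and both inpatient units and the ambulatory surgery center are included. The mix of admissions could therefore differ between 2015 and the later period for reasons unrelated to the study.

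Age, comorbidity and reason for admission can plausibly affect length of stay, falls and delirium. A crude test asks whether two groups of patients differ. Ho2 and Ho3 ask whether the program or the watch made the difference. Without adjustment, even the part of the gap that recorded factors could explain stays in the estimate.

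**Working it through.** **The plan's own figure.** 150 + 150 = 300 agrees with the stated total. It is a convenience sample with no alpha, power, effect size or SD, so there is no power calculation to reproduce.

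**Inputs.** From the documents: n = 150 per cohort, two-sided tests. Assumed, because the documents give no value: alpha 0.05; a continuous outcome scaled to SD 1; no true effect; one prognostic index, built from recorded baseline factors, that differs by d SD between cohorts and explains a share R² of the outcome variance.

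**Formulas.**
- Bias of the crude difference = d × √R²
- SE = √(2/150) = 0.1155 SD
- Shift = bias / SE
- False-positive rate = Φ(shift − 1.96) + Φ(−shift − 1.96)

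| d (SD) | R² | Bias (SD) | Shift | False-positive rate |
|---|---|---|---|---|
| 0.2 | 0.1 | 0.2 × 0.316 = 0.063 | 0.55 | 8.5% |
| 0.3 | 0.2 | 0.3 × 0.447 = 0.134 | 1.16 | 21% |
| 0.5 | 0.3 | 0.5 × 0.548 = 0.274 | 2.37 | 66% |

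For scale, the difference detectable with 80% power is (1.96 + 0.84) × 0.1155 = 0.32 SD. The middle bias is 0.134 / 0.32, about two fifths of that.

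**Does adjustment help?** A simulation with 4,000 runs per setting used one measured confounder, shifted by 0.2, 0.3 or 0.5 SD and correlated 0.2, 0.3 or 0.5 with the outcome, again with no true effect. The crude t-test rejected in about 7% to 58% of runs. A linear model that included the confounder rejected in 4.6% to 5.6%, close to nominal. This shows what adjustment does for a factor that is measured and correctly modelled. It says nothing about factors that are not.

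**The case against.** **The affected endpoints are secondary and the design is openly observational.** This is true, and the primary endpoint is untouched. But Ho2 and Ho3 are formal hypotheses that rest on these endpoints, and calling a study quasi-experimental does not control confounding.

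**The plan allows choice as appropriate.** That phrase selects among the named tests. It does not bring in adjustment, and covariates chosen after the data are seen would invite selective reporting.

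**The figures are assumed.** This stands. No imbalance, R² or alpha is documented, and five of the seven endpoints are counts rather than continuous. A reader might take 21% as this trial's error rate, which the documents do not support.

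**The covariates may not exist for both cohorts.** This also stands. A reader might infer from Measurements that every item is recorded for all 300 patients. That list does not separate the cohorts. PD Medication Reconciliation describes the study team's reconciliation as part of prospective enrolment, and the 2015 data come from EPIC. A covariate measured differently by phase can add bias.

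**Doses per day as a severity marker.** A reader might also infer that the admission list gives the number of scheduled PD doses per day. Measurements names only a list and a total count. A dose count taken from inpatient orders could itself be changed by the intervention, since order time is among the outcomes in Ho2 and Ho3.

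**Precision.** A reader might expect adjustment at R² = 0.2 to be worth 25% more patients (1/0.8 = 1.25). That holds at most for a linear model with balanced groups. It does not carry over to count models or weighting.

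**Adjustment will not rescue the causal claim.** This stands in part. It leaves selection by consent, alertness and watch wearing, and the calendar gap: 2015 data against a protocol version dated 5/9/2019. Because the prospective period starts only once both the education and the watch are in place, one phase coefficient cannot separate Ho2 from Ho3. These are reasons to state limits, not to leave measured confounding uncorrected.

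**Conclusion.** The concern holds. As written, the plan has no prespecified adjustment for baseline factors that its own case report form lists, in a comparison that nothing balances. Measured case-mix differences can therefore be reported as an effect of the intervention on any of the seven patient endpoints.

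Under the stated assumptions the false-positive rate runs from near nominal (8.5%) to 66%. The direction and size in this study are unknown. The documents do not show that the cohorts are in fact imbalanced, that every covariate is available for 2015, or that an adjusted analysis would be free of confounding.

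**What to change.** In Data Analysis, make the main analysis of each patient endpoint a prespecified regression on phase plus age, sex, primary diagnosis (Parkinson's disease or other) and comorbidity count. Add number of admission medications if it is available and measured comparably in the 2015 EPIC extract.

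- Length of stay: log-linear or gamma model.
- Counts: negative binomial model.
- Medication timing: linear model.
- Sparse endpoints, which may include falls: propensity (overlap) weights from the same covariates.

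Report baseline balance by cohort and adjusted differences with 95% confidence intervals. Keep the crude tests as supportive. Do not adjust for PD doses per day unless the count comes from the pre-admission regimen in both cohorts.

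In Limitations, state that adjustment covers measured factors only; that selection by consent, alertness and watch wearing remains, as does the calendar gap; and that the program effect (Ho2) cannot be separated from the WatchRx effect (Ho3).

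The cost is SAP wording, some extra programming in the SAS software already planned, and confirmation that the covariates exist for 2015. The downside is modest model dependence.

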## Measurements

The following will be documented on a case report form: demographics (age, sex, and race), comorbidities and complications, date of discharge, length of stay, and number of medication discrepancies.

- Subject ID (coded de-identified patient identifier)
- Demographics (age race, gender)
- Primary Diagnosis
- Comorbidities
- Medication list at admission (Admission Medication Reconciliation)
  - Number of medications at admission
- Prescribed Medication List (Medication Administration Record)
  - Number of medications during hospitalization
- Medication list at discharge (Discharge Medication Reconciliation)
- Complications associated with medication administration
- Medication Administration Schedule
  - Order Time
  - Patient Falls
  - Number of falls
  - Time of patient falls
  - Injury
- Length of Stay

## **Data Management**

All data in this study will be obtained from multiple sources: EPIC Hyperspace for medical record number. A database in Microsoft Office Excel (Microsoft Corporation, Redmond, WA,

USA) will be created based on a case report form. Data from the WatchRx smartwatch and the WatchRx app will be stored in real time within a secure database. All study data will be imported into SAS software where data management programming will be utilized to flag and generate queries on out of range data issues until they are resolved. All analysis will be performed using SAS version 9.4 (SAS Institute Inc. Cary, NC, USA).

## **Discomforts and Risks**

This study involves no more than minimal risks. No medical intervention is included as part of this study. All patients will be provided and treated as per physician order.

## **Benefits**

This study will improve timely administration of medications to PD patients. Patients enrolled in the study will have direct monitoring of their medication compliance and adherence. This study will improve knowledge of Parkinson's disease amongst clinicians and better medication management of PD patients.

## **Limitations**

Limitation 1: Single site

Limitation 2: Convenience sample

## **Confidentiality**

Data will be handled in a confidential manner to meet mandated IT Security standards and to prevent loss of privacy.

All electronic files will be stored in an encrypted and password-protected database on a secure medical center server. Only co-investigators, advanced practice nurses and the data coordinator who contact the subjects will have access to information linked to subject identifiers.

- Each eligible patient will be assigned a study specific identification number (ID#) to separate patient information from their specific study data and responses. Any research data extracted from participants' medical records will be recorded in a study specific electronic spreadsheet and coded with participants' ID#'s. The electronic spreadsheet will be kept on a password protected computer.
- The key linking ID numbers to patients' identifier will be kept on a password-protected computer.
- Publication resulting from this research will not contain any information that could potentially identify participants either directly or indirectly.

## Appendix A – PD Knowledge Assessment Survey

 Where medicine meets innovation	The PICK Study Parkinson's Disease Inpatient Clinical Knowledge and Management	Role:  APN  Physician Ad  Staff Nurse  Case Manager  Physician  Pharmacist  PA  Other, specify _____
--	---	---

**Parkinson's Disease Knowledge Assessment**

**01.** • Please select the correct answer.

In most cases PD is caused by:

- a. There is no known cause
- b. Smoking
- c. Genetics
- d. Environmental toxins

**02.** Which is not a cardinal sign in the motor aspect of PD?

- a. Slowness of movement
- b. Tremor
- c. Rigidity of muscles
- d. Muscle weakness

**03.** Select the incorrect statement.

PD is found:

- a. In all ages
- b. In all races
- c. In both genders
- d. In males only

**04.** Please select the correct answer.

Which neurotransmitter is depleted in patients with PD?

- a. Serotonin
- b. Acetylcholine
- c. Dopamine
- d. Norepinephrine

**05.** Which of the following brand name drugs contain levodopa, the precursor to dopamine?

- a. Comtan
- b. Sinemet
- c. Symmetrel

**06.** What type of food can interact with the adsorption of PD medication?

- a. Fats
- b. Carbohydrates
- c. Protein
- d. Sugars

**07.** Select the drug which is contraindicated in PD patients:

- a. Quetiapine (Seroquel)
- b. Haloperidol (Haldol)
- c. Trimethobenzamide (Tigan)
- d. Ibuprofen (Motrin)

**08.** Select the correct answer.

Tremor in PD is most commonly seen in patients:

- a. On action
- b. On posture
- c. At rest
- d. When asleep

**09.** Please select all the correct answers which can apply to PD patients:

- a. Anxiety
- b. Constipation
- c. Sexual dysfunction
- d. Postural hypotension

**10.** Select the incorrect answer.

Nursing care of a patient with PD includes:

- a. Ensuring contraindicated medications are avoided
- b. Sitting patient upright for meals

d. Requip

c. Restraints for patients with severe tremors

d. Ensuring medications are given on time

## Parkinson's Disease Knowledge Assessment

**11.** Please select the term which does not apply.  
PD is a disease which is:  
 a. Degenerative  
 b. Reversible  
 c. Progressive  
 d. Made worse by stress

**12.** Select the correct answer (s).  
Dyskinesia describes involuntary chorea-like movements of the head, shoulders, trunk or limbs. In PD it:  
 a. is a side effect of medication  
 b. is a symptom of the condition  
 c. requires patient restraint  
 d. it is a precursor to seizures

**13.** Bradyphrenia refers to:  
 a. Hallucinations in PD  
 b. Depression in PD  
 c. Slowness in thinking in PD  
 d. Psychosis in PD

**14.** Patients with PD can tolerate missing their medications:  
 a. up to 30 minutes  
 b. One hour or more  
 c. No more than fifteen minutes  
 d. can take two doses on the next schedule

**15.** Select the incorrect statement.  
 a. The presence of tremor is necessary for the diagnosis of PD  
 b. PD can affect any age  
 c. PD can be hereditary  
 d. PD medications slow down the disease progression

**16.** Select the drug which is contraindicated in PD patients:  
 a. Metoclopramide (Reglan)  
 b. Acetaminophen  
 c. Ondansetron (Zofran)  
 d. Oxycodone

**17.** Select the incorrect answer  
 a. PD is a form of dementia  
 b. Cognitive slowing can be a side effect of PD meds  
 c. Vivid dreams can occur for patients with PD  
 d. Response to PD meds can be affected by type of food

**18.** Delay in PD medication administration can lead to all the following except:  
 a. falls  
 b. confusion  
 c. seizures  
 d. dysphagia

**19.** Please select the correct answer(s)  
 a. All PD patients have dementia  
 b. PD patients may have both motor and non-motor symptoms  
 c. Strict adherence to medication timing is not crucial for PD patients  
 d. PD can be diagnosed by a blood test

**20.** Please select which medication is safe in PD  
 a. Meperidine (Demerol) put an R sign for registered trademark  
 b. Prochlorperazine (Compazine)  
 c. Clonazepam (Klonopin)  
 d. Promethazine (Phenergan)

PICK STUDY - PD Clinician Assessment Education Questionnaire

Adopted with Permission From v06.11.2015

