## **Primary Endpoints**

Difference in PD Knowledge assessment score before and after Parkinson's Disease Inpatient Clinical Knowledge and Management Program (Appendix A- PD Knowledge assessment score).

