**CONFIDENTIAL**

## Appendix B – PD Inpatient Clinical Knowledge and Management Study (PICK)

### Education Plan Overview

Prior to launch of the educational plan, there will be Nursing Grand Rounds. The curriculum will also be introduced to case managers, pharmacists, physical and occupational therapists and dieticians. Clinical Level III and IV registered nurses on each unit will be designated with the responsibility of steering the education on the unit. They will be directly supported by Nurse Educators and the Department of Neurosurgery clinicians.

The educational plan will be rolled out by direct testing, education and retesting to each nursing unit with distribution via print material and electronic material. Contact hours will be awarded for those completing the pre-test, webinar and post-test.

**Step 1:** Administration of a Parkinson's disease knowledge base assessment test to the target audience via HOLA.

**Step 2:** Introduction of the PD webinar through HOLA. During this step, there will also be posters and other educational material available to the units.

**Step 3:** Re-administer the Parkinson's disease knowledge base assessment test to determine retention.

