## Appendix E – Educational Information on PD Medication

THIS PATIENT HAS PARKINSON'S DISEASE		
To Avoid Serious Side Effects Please Make Sure Parkinson's Medications are given		
ON TIME, EVERY TIME!		
(Within 30 Minutes)		
COMMON PD MEDS	CONTRAINDICATED MEDICATIONS	
Sinemet (Carbidopa/Levodopa)	Prochlorperazine (Compazine) Cyclobenzaprine (Flexeril)*	
Selegiline (Eldepryl)	Promethazine (Phenergan) Tramadol (Ultram)*	
Rasagiline (Azilect)	Metoclopramide (Reglan) Haloperidol (Haldol)	
Amantadine (Symmetrel)	Meperidine (Demerol) Fluphenazine (Prolixin)	
Comtan (Entacapone)	Methadone * Chlorpromazine (Thorazine)	
Requip (Ropinirole)	Droperidol	
Mirapex (Pramipexole)	* If on Selegiline or Rasagiline	
Stalevo (Carb/Levo/Entacapone)		

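### Item 15 of the primary knowledge test may have two defensible answers where one is asked for, and item 14's key must be reconciled with Appendix E; at most 2 of 20 items are affected, in either direction.

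*Combined protocol and SAP*

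**What the plan says.** The Primary Endpoints section defines the endpoint as "Difference in PD Knowledge assessment score before and after Parkinson's Disease Inpatient Clinical Knowledge and Management Program", measured with the Appendix A survey. The Education Plan Overview in Appendix B has staff take the test, see the webinar and take the test again: "Re-administer the Parkinson's disease knowledge base assessment test to determine retention". The Knowledge Assessment Methodology adds a further post-test four months after the webinar.

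Item 15 carries the instruction "Select the incorrect statement", in the singular. Its option a reads "The presence of tremor is necessary for the diagnosis of PD" and its option d reads "PD medications slow down the disease progression". Items 9, 12 and 19, by contrast, openly allow more than one answer.

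Item 14 has the stem "Patients with PD can tolerate missing their medications". Option a allows 30 minutes, and option c reads "No more than fifteen minutes". The teaching sheet in Appendix E gives "Within 30 Minutes".

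The text available for review shows no answer key, item weights or scoring rule for the survey. A key may exist with the survey's source.

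**The concern.** A defect in an item enters the primary result directly, because the score change is the endpoint and the same items are used on each occasion. If two options of a one-answer item are both incorrect, no single key is valid. A clinician who knows that both are incorrect has to guess which one the test's author had in mind. Such a clinician can lose a point held at the pre-test or gain one by luck, and neither change reflects learning.

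Item 14 raises a different question, which is whether the credited answer agrees with the timing that staff are shown. Appendix E and the fifth learning objective in Appendix B share the same slogan on punctual dosing, which ties the sheet to the teaching. A clinician taught from it has a reason to choose the 30-minute option, and nothing visible in the plan ensures that this is the credited one.

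**Working it through.** **Plan's own figure.** The sample column of Table 1 (Sample Size Calculation) sums to 100 + 87 + 48 + 19 + 40 + 17 + 12 + 17 + 6 = 346, which matches the stated number of clinicians. It is a count of a convenience sample. The plan gives no alpha, power, effect size or SD for the knowledge score.

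**Assumptions.** One point per item; an informed clinician chooses evenly between 15a and 15d; two-sided alpha 0.05; 80% power; all 346 clinicians give paired scores; SD of change 2 to 4 points.

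**Item 15.** Suppose that a and d are both incorrect and one of them is keyed. A clinician who knows this after the Program has an expected credit of 0.50.

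| Pre-test answer | Expected credit before | Expected credit after | Change |
|---|---|---|---|
| The keyed option | 1.00 | 0.50 | -0.50 |
| The other defensible option | 0.00 | 0.50 | +0.50 |
| Guess among four | 0.25 | 0.50 | +0.25 |

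A sound item would give 1.00 - 0.25 = +0.75 for a move from guessing to knowing. The shortfall is therefore 0.75 - 0.25 = 0.50 point. If the split is uneven and a share p of informed clinicians choose the keyed option, the shortfall is 1 - p.

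**Item 14.** Take a clinician who answers with the sheet's figure after the Program.

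| Keyed option | Pre-test answer | Change |
|---|---|---|
| a (30 minutes) | a | 0 |
| a (30 minutes) | c | +1 |
| c (fifteen minutes) | a | 0 |
| c (fifteen minutes) | c | -1 |

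From a four-way guess, the change is 1 - 0.25 = +0.75 if a is keyed and 0 - 0.25 = -0.25 if c is keyed. Only a key of c produces a conflict with the sheet.

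**Bounds.** Two of 20 items are 10% of the scale. The most adverse combination for one clinician has an expected change of -0.5 - 1 = -1.5 points, and -2 points at worst. It requires c to be keyed on item 14 and the keyed option to have been chosen on both items at the pre-test.

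**Yardstick.** Detectable mean paired change = (1.96 + 0.84)/√346 = 2.80/18.60 = 0.151 SD. For an SD of change of 2, 3 or 4 points this is 0.30, 0.45 or 0.60 points. If every clinician moved from guessing to full knowledge on item 15, the mean shortfall of 0.50 would fall within that range. If 30% did so (an illustration), it would be 0.30 × 0.50 = 0.15 points, below the range.

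**The case against.** A reader might infer three stronger things, and the documents support none of them.

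- **That item 15 demonstrably contains two false statements.** No section gives a truth value for a or d, and the webinar's content is not in the text. Item 2 lists tremor among several motor-sign options and item 11 concerns the course of the disease; neither settles the matter. What stands is that both options are defensible on ordinary clinical judgement, and that the wording allows only one answer.
- **That item 14 contradicts Appendix E.** Its option a carries the sheet's figure, and a wrong option with another figure is normal in multiple choice. The two texts also differ in kind: the item asks what patients tolerate, whereas the sheet reads as a bedside notice on giving medication. What stands is a conditional conflict that depends on the key.
- **That learning will be scored as lost knowledge.** The tables above show false gains as well as false losses.

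It is also fair to say that the size is a ceiling case. It rests on an assumed scale, alpha, power and SD, and on 346 paired scores, although the Data Analysis section names only tests for independent groups. The expected total gain is unknown, and gains on the other 18 items could outweigh both items. These points limit the importance of the finding, but they do not supply a valid single key for item 15.

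**Conclusion.** The point holds in a limited form. Item 15 asks for one answer where two are defensible, subject to confirmation by the study's neurology clinicians, so a single key can mis-score informed clinicians at either occasion and in either direction. Item 14 and Appendix E must be reconciled; this review takes no view on which timing is right.

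At most 2 of 20 items are touched. With one point per item and an even split between a and d, the shortfall on item 15 averages at most about 0.5 point per clinician, and only if clinicians move from guessing to full knowledge. The sign and size of the net effect on the primary result cannot be determined without the key and the pre-test answers. This is a correctable weakness in the primary instrument. It does not show that the primary comparison is invalid.

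**What to change.** 1. Have the study's neurology clinicians confirm the status of 15a and 15d. If testing has not begun, reword item 15 so that exactly one statement is false.
2. If tests have already been taken, credit either a or d in the same way at every occasion. This removes the false loss, but a four-way guess then earns 0.50, so the gain from guessing to knowing is 1.00 - 0.50 = +0.50 instead of the +0.75 of a sound item.
3. Reconcile item 14 with Appendix E, then lock one key for the pre-test, the post-test and the four-month test.
4. Report the primary change with all 20 items and again without items 14 and 15.

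The cost is an edit to two items and the key in the learning system, or a re-scoring of stored item-level answers, with no extra participants. The score departs slightly from the adopted survey. Rewording may need the permission of the survey's owner, whereas re-scoring does not change the instrument. Reporting the full 20-item score alongside keeps most of the comparability.
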